7.4 Data Source

The data to be collected in the study will be obtained from patients' registry, from electronic medical records and manual medical records. Data collection processes consist of this following process:

1. Data checking (editing)

This is an activity to check the research data form sheet for data completeness so that if there are any discrepancies it can be completed immediately by the researcher.

2. Giving code (coding)

The activity of changing data into numbers/numbers.

3. Entering data into a computer program (data entry)

This is an activity of processing data obtained from research data forms and then analyzing it by entering the data into a computer program.

4. Cleaning data (cleaning)

Data cleaning activities were carried out to check again before further analysis was carried out.

All data collected during this study must be documented on an ongoing basis in a complete, accurate, eligible, and timely fashion. The data in the eCRF should be consistent with the relevant source documents.

7.5 Study Size

The sample size was determined based on time, namely all data on adult heart surgery patients between January 1, 2020 - December 31, 2022, who were selected based on acceptance criteria.

7.6 Data Management

The main purpose of the eCRF is to obtain data required by the non-experimental study protocol in a complete, accurate, legible, and timely manner. The data in the eCRF should be consistent with the relevant source documents.

Data protection and privacy regulations will be implemented in capturing, forwarding, processing, and storing subject data.

7.7 Statistical Analysis Plan

All analyses will be performed on patients who underwent cardiac surgery in period between 1 January 2020 until 31 December 2022, with complication of acute kidney injury (AKI) postoperative. All data were retrieved from patient medical record retrospectively. There were no active observation or data retrieved directly from patients.

Data analysis will be carried out by the statistical team after the research samples have been taken and the data has been completed. The analysis was carried out using SPSS Version 29. and all statistical analysis plans have been completely documented in this statistical analysis plan.

Data that has been processed correctly is then analyzed by:

- a. Univariate analysis

This univariate analysis was carried out to obtain an overview of the frequency distribution of research subjects and the distribution of the proportion of cases and controls according to each independent variable (risk factor) studied.

- b. Bivariate analysis

Bivariate analysis was used to determine the relationship between the main risk factors and the incidence of death in hospital while also testing the research hypothesis using the chi square test.

c. Multivariate analysis

Multivariate analysis is carried out with the aim of describing the relationship between the dependent variable and the independent variable simultaneously in the population. Multivariate analysis was carried out by connecting several independent variables with one dependent variable simultaneously. Because the independent variables are categorical, logistic regression was used for the analysis.

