6.1 Primary Objective

- To analyze the association between AKI with RRT and intra-hospital postoperative mortality in cardiac surgery patients compared with AKI patients without RRT

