7.1 Study Design

This research is a non-experimental study with a retrospective cohort analysis design. Data were secondary collected from patient's registry.

The dependent variable is intra-hospital post-surgical mortality, while the independent variables are cardiac surgery patients with complication of Acute Kidney Injury (AKI) and Renal Replacement Therapy (RRT).

[figure not shown]
Analysis was carried out to determine the relationship between these variables.

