7.7.2 Statistical Methods

The statistical analyses described in this section will be performed as further outlined in the SAP, which will be finalized prior to database lock and will be included in the clinical study report for this protocol. The final SAP will take into account any amendment to the protocol.

General Statistical Methodology:

Descriptive statistics (mean, SD, median, interquartile range) will be provided for continuous variables according to the results of data normality tests. Frequencies and percentages will be presented for categorical and ordinal variables.

All analyzes will consider the security of the dataset.

Primary Outcome Analysis:

The primary outcome in this study is to look at the incidence of death in the treatment of patients who have kidney problems with CRRT or not.

Bivariate analysis was carried out using the chi square/fisher's exact test to see whether there was a difference in the incidence of death in treatment between groups (CRRT vs Non-CRRT)

which was then continued to the multivariate analysis stage if it had a p value <0.25 , multivariate analysis was carried out using regression multiple logistics with a significance level of 0.05 which shows that it is a variable that influences the incidence of death in care.

Secondary Endpoint Analysis:

The secondary outcome in this study is to look at the factors causing CRRT in patients undergoing cardiac surgery with AKI.

Bivariate analysis was carried out using the chi square/ Fisher's exact test to see whether there were differences in patient characteristics between patients who were given CRRT and those who were not, which was then continued to the multivariate analysis stage if it had a p value <0.25 . Multivariate analysis was carried out using multiple logistic regression with The significance level is 0.05 which shows that it is a variable that influences the incidence of CRRT use.

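### Sections 7.7 and 7.7.2 disagree on whether a crude chi-square or an adjusted logistic model decides the primary question, and RRT reaches the adjusted model only if its crude p-value is below 0.25

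*Combined protocol and SAP*

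**What the plan says.** Section 7.1 describes the design: "This research is a non-experimental study with a retrospective cohort analysis design". RRT was therefore not assigned by the study. The primary objective (6.1) compares in-hospital death in AKI patients with and without RRT.

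The analysis of that contrast is described in two places.

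- **Section 7.7.** Part (b) relates the main risk factors to in-hospital death, "while also testing the research hypothesis using the chi square test". Part (c) then gives the logistic model a descriptive purpose: "Multivariate analysis is carried out with the aim of describing the relationship between the dependent variable and the independent variable simultaneously in the population". No p-value screen is mentioned here.
- **Section 7.7.2, Primary Outcome Analysis.** Chi-square or Fisher's exact compares deaths between the CRRT and non-CRRT groups, "which was then continued to the multivariate analysis stage if it had a p value <0.25". The next words are "multivariate analysis was carried out using regression multiple logistics with a significance level of 0.05", and the conclusion about influence on death is attached to that model. The chi-square has no significance level of its own.

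I treat RRT and CRRT as the same contrast for this point. Neither section names the adjusted RRT odds ratio as the primary estimate, exempts RRT from the 0.25 screen, fixes a confounder set, or says what happens if the crude and adjusted results differ.

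**The concern.** The protocol expects confounding. Section 5 calls dialysis-requiring AKI the most severe stage, says other factors also raise mortality, and cites a cohort in which EuroScore, bleeding and ventilation time were independent predictors of death. A crude table cannot separate RRT from the severity that led to it.

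Two things are at stake:

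- If the result is significant in the crude table but not after adjustment, 7.7(b) supports one conclusion and 7.7.2 the other. The choice would be made after the data are seen.
- A 0.25 screen is a familiar device for choosing covariates. Here it is applied to the exposure of interest. A crude p of 0.25 or more ends the primary analysis with no adjusted estimate or interval, although that estimate is what a reader of an observational comparison needs.

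**Working it through.** **No design figure to reproduce.** Section 7.5 says "The sample size was determined based on time, namely all data on adult heart surgery patients between January 1, 2020 - December 31, 2022"; it gives no number of patients, expected deaths or power. The sizes below rest on assumptions.

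**Assumed inputs.** No RRT effect; 600 or 1,000 AKI patients; RRT share 8% (inside the 1-10% cited in sections 4 and 5); one binary confounder present in 60% of RRT and 25% of non-RRT patients; mortality 8% without the confounder; confounder odds ratio for death 2 or 3.

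**Step 1: crude mortality created by confounding alone.** Mortality with the confounder is o/(1+o), where o = OR × 0.08/0.92.

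- OR 2: 0.148. RRT group 0.6×0.148 + 0.4×0.08 = 0.121; non-RRT group 0.25×0.148 + 0.75×0.08 = 0.097. Crude odds ratio 1.28.
- OR 3: 0.207. RRT group 0.156; non-RRT group 0.112. Crude odds ratio 1.47.

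**Step 2: how often the chi-square rejects at 0.05.** With difference d, pooled standard error s0 and unpooled standard error s1, the chance is about Φ((d − 1.96·s0)/s1) + Φ((−d − 1.96·s0)/s1).

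- OR 2, n = 600 (48 RRT patients): d = 0.0239, s0 = 0.0449, s1 = 0.0487; about 10%.
- OR 3, n = 1,000 (80 RRT patients): d = 0.0444, s0 = 0.0372, s1 = 0.0419; about 25%.

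Simulation of the four combinations gives 11-24%, in agreement with these approximations.

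**Step 3: the sequence in 7.7.2.** It rejects only if crude p < 0.25 and adjusted p < 0.05, so it cannot reject more often than the same adjusted test without the screen. Simulated rejection:

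| Procedure | Rejects with no RRT effect |
|---|---|
| Chi-square alone (one reading of 7.7(b)) | 11-24% |
| Screen at 0.25, then adjusted test (7.7.2) | 3.8-5.1% |
| Adjusted test, no screen | 4.5-5.2% |

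**Step 4: how often the screen removes the adjusted estimate.** Replacing 1.96 by 1.150 (two-sided 0.25) in the step 2 formula, the screen is passed in 34% (OR 2, n = 600) to 53% (OR 3, n = 1,000) of studies. No adjusted RRT estimate is produced in 1 − 0.53 = 47% to 1 − 0.34 = 66%.

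If RRT mortality is instead near the cited 174/412 = 42.2%, and non-RRT mortality is assumed to be 5-20% with 300-1,200 patients, the screen is passed in about 77-100% of studies at an RRT share of 5-10%. At a share of 1% the figure is about 44-98%, a rough approximation with only 3-12 RRT patients.

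**Step 5: sensitivity to the assumptions.** With 300-1,200 patients, RRT share 5-10%, confounder prevalence 30%, mortality without RRT 10%, and a confounder odds ratio of 2 to 6 with both RRT and death, the chi-square rejects in 5.5-69%. The adjusted test (stratified on the confounder) rejects in 3.9-5.1%.

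**The case against.** The strongest reply is that 7.7.2 is the specific text for the primary outcome and should govern. It gives the 0.05 level and the conclusion to the logistic model alone, and 7.7(b) is a general outline. Any crude p below 0.05 is also below 0.25, so a significant crude result always goes on to adjustment and a reader would see it vanish.

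Much of this stands. A reader might infer that the primary conclusion will rest on a confounded test, or that the plan carries a false-positive rate of 11-24%. The documents do not support either inference: the 7.7.2 sequence keeps the rate near 5% under the same inputs. The reply does not remove the conflict, however. Section 7.7(b) still attaches the hypothesis test to the chi-square, and no sentence gives 7.7.2 precedence.

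A second reply is that RRT will almost surely pass the screen. That is likely if its mortality is near the cited 42.2% and RRT patients are not very few. A reader might also infer that the screen will often hide a real effect through negative confounding. The documents point to upward confounding, since RRT marks the most severe cases. Under an assumed strong masking confounder (odds ratio 0.25 with RRT, 4 with death) and a true RRT odds ratio of 2-3, the screen blocked a significant adjusted result in 1.4-16.7% of simulated studies. That is possible, but not the expected case.

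A third reply is that 7.7.2 mentions a SAP still to be finalised. Section 7.7, however, says that the plans are fully documented here. A final SAP would be a convenient place for the correction.

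**Conclusion.** The point holds as a conflict between two sections together with a screen wrongly applied to the exposure of interest. If the chi-square decides, about 11-24% of null studies would be declared positive under the assumed inputs, and 5.5-69% over the wider set. If the 7.7.2 sequence decides, the error rate is near 5%, but only when the confounder is measured and correctly modelled. The cost of that reading is that RRT has no adjusted estimate whenever crude p is 0.25 or more: 47-66% of null studies under the first set of inputs, and far fewer if RRT mortality is as high as cited. None of these percentages is a document figure. They show direction and plausible range. The conflict and the missing rule for RRT rest on the text alone.

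**What to change.** In both 7.7 and 7.7.2, state that:

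1. The primary estimate and test is the RRT odds ratio, with 95% CI, from a multiple logistic model for in-hospital death.
2. RRT stays in that model whatever its bivariate p-value; the 0.25 screen does not apply to it.
3. The model adjusts for named baseline confounders fixed before analysis and already listed in Table 7.2, for example age, type of surgery, diabetes, hypertension, pre-operative creatinine, history of renal disease and history of stroke. Their number should be limited to what the count of deaths supports.
4. The chi-square or Fisher result is descriptive.

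It is not enough to refer to a prespecified adjusted model. The plan does not contain one, because 7.7.2 selects variables by p-value and Table 7.2 mixes baseline items with postoperative ones such as prolonged ventilation and ICU stay. The covariates have to be chosen and written down.

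The cost is that short decision, a few sentences of text, and possibly a slightly wider interval. No new data are needed.

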[name], MD	Address: [name] [contact] [name] Email : [contact]

Contributing Investigators

1. [name] MD Address:Department of Perioperative Intensive Care and Non-Surgical Anaesthesia
[name]
ORCID ID : [name]
2. [name] MD. Address:Department of Perioperative Intensive Care and Non-Surgical Anaesthesia
[name]
ORCID ID : [name]
3. [name] MD Address:Department of Perioperative Intensive Care and Non-Surgical Anaesthesia
[name]
ORCID ID : [name]
4. [name] MD Address:Department of Perioperative Intensive Care and Non-Surgical Anaesthesia
[name]
ORCID ID : [name]

4 Abstract

The prevalence of acute kidney injury (AKI) varies up to 30% in post-cardiac surgery patients. Of the patients who suffer from AKI, around 1 - 10% will require renal replacement therapy (RRT). Cardiac surgery associated-AKI patients who require renal replacement therapy/dialysis have higher risk of mortality. The purpose of this study was to assess the risk of AKI-RRT on intrahospital mortality, and other factors that have an association with postoperative mortality. The method was non-experimental research design as retrospective cohort analysis. Dependent variable, in-hospital mortality was determined first and then the independent variables were examined to see the relationship between the variables.

Keywords: Acute Kidney Injury (AKI), Renal Replacement Therapy (RRT), cardiac surgery, intrahospital mortality

5 Rational and Background

The overall incidence of mortality post-cardiac surgery in some literatures varies between 2-8%. Cardiac surgery associated - acute kidney injury (CSA-AKI), a common postoperative complication, has increased risk for post-operative mortality. The incidence of mortality in patients complicated with CSA-AKI is up to 60%. The most severe stage of CSA-AKI, which requires dialysis therapy, is an independent risk factor. The prevalence of acute kidney injury is ranged up to 28% in cardiac surgery patients, of which around 1 – 10% of those patients required renal replacement therapy (RRT).¹⁻⁵

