The term of Acute Kidney Injury was developed by the Kidney Disease Improving Global Outcomes (KDIGO) organization in 2012, which is defined it as a sudden decrease (≤ 24 hours) in renal function characterized by an increase in serum creatinine (≥ 0.3 mg/dL or $\geq 50\%$ [1.5 times baseline]), or reduction in urine output <0.5 mL/kg/hour for >6 consecutive hours. Based on these criteria, AKI stage 3 is categorized as acute renal failure or ARF.^{1, 6, 7}

In a study conducted by Bove *et al.* in 2018, AKI is a serious complication after cardiac surgery that increases the incidence of morbidity and mortality. Renal replacement therapy (RRT) has been used as one of the important therapies in patients with severe AKI. Although the incidence of CSA-AKI requiring RRT is reported in about 1-10% of all AKI events after cardiac surgery, it is also shown that patients with severe AKI who require RRT therapy suffer a higher post-operative mortality rate. Previous studies reported intra-hospital mortality up to 43.5% in patients with AKI-RRT. Recent research found that from 412 CSA AKI-RRT patients, 174 patients (42.2%) died intra-hospital, with a EuroScore > 7 , intraoperative bleeding > 1 liter and mechanical ventilation time > 70 hours as other independent risk factors. Meanwhile, post-operative use of furosemide was considered as protective factor in this study (OR 0.48). This information is similar with the results of our previous study regarding the use of diuretics for CSA-AKI patients.⁸⁻¹¹

Considering the significant impact of AKI on the outcomes of patients' post-cardiac surgery, this study aimed to conduct an analysis of the risk factors that contribute to the incidence of post-operative mortality in patients with CSA-AKI, particularly regarding those cases in stages which required RRT. Based on the above background, this study's primary purposes was to analyze association between patients with CSA-AKI with RRT and in-hospital postoperative mortality risk compared to patients with CSA-AKI without RRT.

Study Rationale

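### Two logistic models start from 16 and 17 candidate parameters with no stated event counts and no sparse-data method; in a small cohort the secondary CRRT model in particular can separate or give inflated odds ratios

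*Combined protocol and SAP*

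**What the plan says.** Section 7.7 restricts every analysis to cardiac surgery patients with postoperative AKI, names SPSS 29, and describes the multivariable step as "connecting several independent variables with one dependent variable simultaneously" by logistic regression. Section 7.7.2 defines two such models. The primary one has death as the outcome. The secondary one has CRRT use as the outcome and begins with a "chi square/ Fisher's exact test to see whether there were differences in patient characteristics" between patients with and without CRRT. In both, variables with bivariate p<0.25 go forward and are judged at 0.05. Fisher's test is the only provision for small cells, and it applies only to the bivariate step.

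On size, section 7.5 says "The sample size was determined based on time", meaning all eligible cases from 2020 to 2022. It gives no expected number of AKI patients, RRT patients or deaths. The background in section 5 cites literature in which "CSA-AKI requiring RRT is reported in about 1-10% of all AKI events after cardiac surgery", and one series where "from 412 CSA AKI-RRT patients, 174 patients (42.2%) died intra-hospital". The abstract repeats the 1-10% share.

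**The concern.** In the CRRT model, patients with RRT are the events. In the death model, RRT is the exposure of interest. If RRT is as uncommon as the cited literature suggests and the AKI cohort is of modest size, cross-tabulations with uncommon covariates (pre-operative creatinine above 3.0 mg/dL, stroke, IABP, the smaller surgery categories) can contain empty cells. An ordinary logistic fit then separates: a coefficient runs off to infinity and its Wald interval is useless. Short of separation, few events push odds ratios away from 1. The plan has no rule for either case, so the analyst would have to improvise after seeing the data. Section 7.7.1 leaves missing values out of the analysis; if that means complete cases, the cells shrink further.

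**Working it through.** The plan states no sample size, event count or power, so there is no figure of its own to reproduce.

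**Parameter count (Table 7.2).** There are 15 variables. AKI is constant in an AKI-only cohort, which leaves 14. Surgery type has five levels, so 4 parameters.
- Death model: 13 binary variables including RRT + 4 = 17.
- CRRT model: 12 binary variables + 4 = 16.

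**RRT events per candidate parameter, CRRT model** = N × RRT share / 16. N is assumed.

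| AKI patients | 1% RRT | 5% RRT | 10% RRT |
|---|---|---|---|
| 500 | 5/16 = 0.3 | 25/16 = 1.6 | 50/16 = 3.1 |
| 1,000 | 10/16 = 0.6 | 50/16 = 3.1 | 100/16 = 6.3 |
| 2,000 | 20/16 = 1.3 | 100/16 = 6.3 | 200/16 = 12.5 |

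**Deaths per candidate parameter, death model, N = 1,000.** Deaths = N × share × 0.422 + N × (1 − share) × m, where 174/412 = 0.422 and m, mortality without RRT, is assumed to be 3-10% because the document gives no such rate.
- Lowest: (10 × 0.422 + 990 × 0.03)/17 = 33.9/17 = 2.0.
- Highest: (100 × 0.422 + 900 × 0.10)/17 = 132.2/17 = 7.8.
- At 1% RRT only about 10 × 0.422 ≈ 4 of the deaths are in the RRT group.

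**Chance of an empty cell.** A covariate with assumed prevalence 2%, unrelated to RRT, is absent from all n RRT patients with probability 0.98^n. At N = 1,000 this is 0.82, 0.36 and 0.13 for n = 10, 50 and 100.

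**Can the screen admit a separating variable?** Yes. With the covariate present in 0 of 50 RRT patients and 48 of 950 others, Fisher's p is 0.17. The variable passes at 0.25, and its maximum-likelihood odds ratio is zero. Surgery type could likewise pass on an overall p-value while one of its five categories is empty.

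**Simulated separation, CRRT model, as % of fits at 1/5/10% RRT.** Two separate simulations, each with its own assumed prevalences and effects:

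| AKI patients | All 16 parameters, first | All 16 parameters, second | After p<0.25, first | After p<0.25, second |
|---|---|---|---|---|
| 500 | 99/58/18 | 92/69/19 | 56/16/7 | 62/20/9 |
| 1,000 | 96/17/2 | 96/19/1 | 23/5/0 | 34/8/0 |
| 2,000 | 80/2/0 | not tabulated | 10/1/0 | about 1 or less at 5-10% RRT |

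The first simulation used 200 runs per full-model setting and 100 per screened setting, with separation flagged when a coefficient exceeded 12 in absolute value. With 100 runs, the standard error at 56% is √(0.56 × 0.44/100) ≈ 5 points. Its screened runs were repeated under a higher assumed death rate, which should not affect the CRRT model. They gave 52/13/8, 34/2/1 and 17/0/0, so differences of this order are noise.

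**Simulated separation, death model after the screen** (RRT forced in, mortality without RRT about 6%): 32/10/9% at 500, 9/1/1% at 1,000 and 0% at 2,000.

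**Firth against ordinary maximum likelihood.** RRT odds ratio in the screened death model, true value about 5.5, 5-95% range over runs:
- 500 patients, 1% RRT: 1.3-40 with Firth, effectively 0-358 with ordinary likelihood.
- 500 patients, 5% RRT: 2.7-12.5 against 2.7-14.5 (medians 6.0 and 6.4).
- 2,000 patients, 10% RRT: 3.9-7.8 against 3.9-8.0.

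**The case against.** The strongest reply is that the plan does not fit all 16 or 17 parameters. After the screen, about 4 to 12 remained in the simulations, and rare covariates with an empty cell often fail to pass. A reader might take the full-model rates (58-69% at 500 patients and 5% RRT) as the plan's failure rate. That is not supported: the screened rate there is 16-20%. The screen reduces separation substantially but does not remove it. The separate objection that screening on the same data spoils later p-values concerns overfitting, not separation.

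Three further inferences go beyond the documents:
- *That the sponsor plans for 1-10% RRT.* The figure is cited background, not a design input. Likewise, ordinary maximum likelihood is inferred from an unqualified reference to logistic regression.
- *That separated variables would be reported as influential.* Under the usual Wald test (the plan names none), the standard error grows with the coefficient. In one check of full-model fits, none of about 575 separated coefficients was significant. The likelier harms are an unusable estimate for a real factor, or an inflated estimate that stops short of separation.
- *That the cohort is too small.* Ten events per parameter would need 160 RRT patients, or 160/0.10 = 1,600 to 160/0.01 = 16,000 AKI patients. That ratio is an outside convention, and the actual cohort size is not stated. With about 2,000 patients and 5-10% RRT the problem is negligible.

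It is also fair to say that the exposed model is a secondary one, that factors leading to CRRT are not among the objectives in section 6, and that Firth estimation cannot create information: a range of 1.3 to 40 is finite but still very wide.

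**Conclusion.** The point stands as a conditional weakness that should be fixed; it does not show that the analysis will fail. The document establishes 16 and 17 candidate parameters, a cited RRT share of 1-10% of AKI patients, no event counts, and no sparse-data provision in the regression models.

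The size of the problem depends on a cohort size that the document does not give. For the CRRT model after the planned screen, about 56-62/16-20/7-9% of fits separate at 1/5/10% RRT with 500 AKI patients, and about 23-34/5-8/0% with 1,000. With 2,000 it is about 1% or less at 5-10% RRT, though still 10% or more at 1%.

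The document does not support reading this as a serious threat to the primary analysis. With 1,000 patients and 5-10% RRT, the death model separates in about 1% of fits. Its weak point is the precision of the RRT odds ratio when few patients had RRT. All separation rates rest on assumed covariate prevalences and effects and indicate order of magnitude only.

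**What to change.** Amend sections 7.7 and 7.7.2 before the analysis:
1. Replace the p<0.25 screen with a prespecified covariate list for each model, with RRT always kept in the death model.
2. Before fitting, tabulate AKI patients, RRT patients and deaths, collapse sparse surgery categories according to the observed event counts, and report the RRT and death counts with the results.
3. Fit both models by Firth penalised likelihood with profile-likelihood confidence intervals.

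Section 7.7.2 says that the SAP will be finalised before database lock, so the change has a place. The cost is a few lines of text and slight shrinkage of the estimates, with almost no difference when data are ample. One practical point is open: the plan names SPSS 29, so the availability of the routine in the sponsor's installation must be checked or other software named.

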6.2 Secondary Objectives

- To analyze the risk of intra-hospital post-surgical mortality in cardiac surgery patients who complicated with CSA AKI
- To compare the risk of intra-hospital post-surgical mortality in cardiac surgery patients who complicated with CSA AKI with requirement of RRT and without RRT
- To Identify and analyze perioperative factors that play an important role in the incidence of mortality in AKI patients after cardiac surgery

7 Research Methods

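### The purpose and secondary objectives ask about mortality risk with and without RRT, but the only adjusted analysis is a logistic model with no named effect measure and no adjusted risks

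*Combined protocol and SAP*

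**What the plan says.** **Objectives.** Section 6 sets the purpose as evaluating the risk of in-hospital death in patients with cardiac-surgery-associated acute kidney injury (AKI) who need RRT, against those who do not. A secondary objective in section 6.2 says the same: "To compare the risk of intra-hospital post-surgical mortality in cardiac surgery patients who complicated with CSA AKI", with and without RRT. The primary objective in section 6.1 is worded differently and asks only for an association.

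**Design.** Sections 7.1 and 7.5 describe a retrospective cohort of all eligible adult patients operated on from 2020 to 2022. Patients are not sampled by outcome.

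**Analysis.** Sections 7.7 and 7.7.2 plan a chi-square or Fisher's exact test, a screen at p < 0.25, and then multiple logistic regression judged at the 0.05 level. The reason for the model is given as "Because the independent variables are categorical, logistic regression was used for the analysis". The abbreviation list in section 2 contains the odds ratio, the risk ratio and the confidence interval, but none of them is assigned to an analysis. Section 7.7.2 does foresee frequencies and percentages for categorical variables.

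**Event rates.** On mortality with RRT, section 5 reports that "from 412 CSA AKI-RRT patients, 174 patients (42.2%) died intra-hospital" and, separately, "Previous studies reported intra-hospital mortality up to 43.5% in patients with AKI-RRT". It gives no figure for AKI patients without RRT.

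**The concern.** An odds ratio is close to a risk ratio only when the outcome is uncommon in both groups. The protocol's own background puts mortality with RRT above 40%. A reader whose question has been framed as risk may take the odds ratio as how many times the risk is raised, and so read the main result as larger than it is.

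Nothing in the design forces this. The patients form a full cohort, so risks, risk ratios and risk differences can all be estimated, and the usual case-control reason for settling for an odds ratio does not apply. The reason given for the model also suggests that the effect measure was not considered. Logistic regression suits this study because the outcome in Table 7.1 is binary, not because the predictors are categorical. Since no measure is named, what will be headlined is left open until the results are known.

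At stake is how the size of the RRT association is reported and read. The significance test and the direction of the association are not affected.

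**Working it through.** **1. Check the cited figure.** 174/412 = 0.4223, which reproduces the 42.2% in section 5.

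**2. Inputs.**
- Mortality with RRT, p1 = 0.422 (section 5, a cited cohort, not a planning value of this study). The upper cited value is 0.435.
- Mortality in AKI without RRT, p0: not in the documents. Assumed, and varied from 2% to 40%.

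**3. Formulas, for crude measures.**
- OR = [p1/(1 − p1)] / [p0/(1 − p0)]
- RR = p1/p0
- Hence OR/RR = (1 − p0)/(1 − p1)

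The ratio depends on both mortalities, so mortality with RRT alone does not fix it.

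**4. Results at p1 = 0.422**, where OR/RR = (1 − p0)/0.578:

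| Assumed p0 | OR | RR | OR/RR | Excess of OR over RR | Risk difference (points) |
|---|---|---|---|---|---|
| 2% | 35.8 | 21.1 | 1.70 | 70% | 40.2 |
| 5% | 13.9 | 8.4 | 1.64 | 64% | 37.2 |
| 10% | 6.6 | 4.2 | 1.56 | 56% | 32.2 |
| 20% | 2.9 | 2.1 | 1.38 | 38% | 22.2 |
| 30% | 1.7 | 1.4 | 1.21 | 21% | 12.2 |
| 40% | 1.10 | 1.06 | 1.04 | 4% | 2.2 |

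At p1 = 0.435 the ratio is 1.68 for p0 of 5%, 1.42 for 20% and 1.24 for 30%.

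**5. Can the documents pin down p0?** The nearest figure is for AKI as a whole: "The incidence of mortality in patients complicated with CSA-AKI is up to 60" percent. If 60% were the actual AKI-wide mortality and a share s of AKI patients had RRT, then p0 = (0.60 − 0.422s)/(1 − s). With s of 1% and 10%, the share range in section 5, p0 is (0.60 − 0.00422)/0.99 = 60.2% and (0.60 − 0.0422)/0.90 = 62.0%. The risk ratio would then be about 0.70 or 0.68, below 1. The 60% is an upper limit, so it does not establish p0. It does show that the documents do not confine p0 to low values.

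**6. Adjusted odds ratio.** The table is for crude measures. A covariate-conditional odds ratio is non-collapsible and can lie further from the marginal risk ratio. As an illustration only, take one standard-normal covariate with an assumed log-odds slope of 1 for death, with marginal risks fixed at 42.2% with RRT and p0 without. The conditional OR is 19.88, 8.88 and 3.56 at p0 of 5, 10 and 20%, against RRs of 8.44, 4.22 and 2.11. The ratios are 2.36, 2.10 and 1.69. A different covariate strength would give different figures.

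**The case against.** **An odds ratio reported as an odds ratio is not an error.** This stands. Section 6.1 asks for an association, and an odds ratio measures one. The harm arises only if it is read as a risk ratio, and section 5 itself labels a cited estimate as an OR. The mismatch is with the purpose and the secondary objectives, not with the primary objective.

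**Absolute risks are already covered.** This stands in part. Section 7.7.2 plans frequencies and percentages and a comparison of deaths between groups, so crude mortality by group should be available, and a crude risk ratio and difference follow from it. What is absent is any adjusted risk.

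**The plan never commits to an odds ratio.** This is also correct. A reader might infer that the odds ratio is the planned adjusted measure. The documents name a model and no measure, so the firm statement is that the measure is unspecified.

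**Standardisation is not clean here.** This stands as a condition on the remedy. The candidate variables in Table 7.2 include ventilation beyond 48 hours and ICU stay beyond 5 days, either of which may follow RRT. Averaging over them would not give a clear comparison of risk with and without RRT.

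**Conclusion.** The point holds as a cheap improvement. The purpose and secondary objectives ask about risk, the cohort can supply it, and the only adjusted analysis is a logistic model with no named measure, no confidence interval and no adjusted risk, risk ratio or risk difference. If the odds ratio becomes the headline, it cannot stand in for a risk ratio when about 42% of RRT patients die.

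The size is conditional. With 42.2% mortality on RRT, the crude excess runs from about 70% to 4% as assumed non-RRT mortality goes from 2% to 40%. A reader might infer a fixed overstatement of some 40 to 65%. At 42.2% that needs non-RRT mortality of about 5 to 19%, and the documents do not give that figure. It would also describe crude measures, not the adjusted one.

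A reader might also infer that logistic regression is the wrong model. It is not: it suits a binary outcome, and only the reason given for it is wrong.

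**What to change.** In section 7.7 and under the primary outcome analysis in section 7.7.2:

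1. Keep the multiple logistic regression and justify it by the binary outcome (died or not died, Table 7.1).
2. Name the adjusted odds ratio for RRT, with its 95% CI, as a reported measure.
3. Beside it, report covariate-standardised in-hospital mortality with and without RRT, their ratio and their difference. Obtain these by predicting each patient's risk from the fitted model with RRT set to yes and then to no, and averaging each set. Give bootstrap or delta-method 95% CIs.
4. Standardise over covariates fixed before RRT. List them in advance and leave out prolonged ventilation and ICU stay, which may follow RRT; the model used for this step should be fitted without those two.
5. Report crude mortality by group, so that the reader can see how far the odds ratio and the risk ratio differ.

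The cost is a few lines of SAP text and a short post-estimation step, with no new data. Section 7.7.2 says the SAP will be finalised before database lock, which leaves room for the change. The downside is a ratio that will look smaller than the odds ratio if mortality is higher with RRT.
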